9 ASSESSMENTS DURING THE STUDY

9.1 BASELINE EVALUATION (visit 0= FIRST VISIT)

After the inclusion of a participant in the study, a comprehensive geriatric assessment will be done with the following parts:

Demographics and epidemiology: Date of birth, age, sex, race, caregiver, marital status, number of persons in the house, and, number of hospitalization in the last year, follow up by others specialist, level of education.

- Medical history

Personal Medical and Surgery History should be recorded in the electronic Case Report Form (eCRF).

- Medications:

In the CRF we register all the regularly medication use (previous hospitalization)

- Functional status

Evaluate functional status with the following scales: Barthel Index, Lawton Index, measures based in performance (SPPB-Short Physical Performance Battery) and PASE Scale, Annex 2.

- Cognitive and depression:

Evaluate the results with MMSE and Geriatric Depression Scale GDS, and delirium risk with CAM scale. See Index 2.

- Physical examination:

Vital signs and physical examination as usual by the clinical investigator.

- Geriatric Syndromes Assessment:

Immobility: Falls and imbalance.

Incontinence: urinary and fecal.

Sensory deprivation

Iatrogenic: Record the numbers of falls during the hospitalization and adverse effects

Pain: assess pain using the VAS Scale. Nutritional Status:

Performed screening for nutritional status using the scale MNA (Mini Nutritional Assessment), Index 2.

- Comorbidities:

Comorbidities will be quantified by Charlson Index, Index 2.

Quality of Life :

The evaluation for the quality of life using the EuroQol five-dimensional (EQ-5D), Index 2.

Caregiver :

- Assessment for the burden of the caregiver; Will be evaluated with The Modified Caregiver Strain Scale. Index 2.

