9.2 EVALUATION AT DISCHARGE FROM THE SPECIFIC CLINICAL SETTING

The following aspects will be assessed:

- Mortality
- Frailty assessment with L. P. Fried's scale and/or FRAIL scale. Functionality assessment with Barthel Index. Indicate the number of hospital stay in days .
- Describe if the patient change the Ward location/ medical /surgical in the hospital (UCI, Coronary unitetc) o)during the evolution in the hospital
- Quantification the number of test (Blood test, urine test, X- Ray, ecography, CT, etc and more specialized like: PET TAC, echocardiography, polisomnography, etc.)
- Quantification the number of consult with other specialist, social worker, palliative care. Etc.
- Usual treatment (Register all the medication at discharge
- Evaluate if the patient develop geriatric síndrome (page 22).
- Destination at dischargeia. (Nursing home, follow up by home care team, I HUG- GRT, day hospital, rehabilitation at home , specialist consultation, etc.)
- Evaluate the perception of the quality of life with the scale EuroQol five-dimensional (EQ-5D).
- Burden of the caregiver with the Economics questionnaire s.
- Economics evaluation Index 3

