9.3 EVALUATION AT 3 MONTHS OF DISCHARGE

Re-evaluate the following aspects by phone :

- Mortality
- Functionality data (Barthel index , Lawton index , PASE Scale).
- Usual medication.
- Residency at the moment.
- Frailty with the FRAIL scale..
- Data of quality of life with the scale EuroQolfive-dimensional (EQ-5D)
- Number of hospitalization and ER, indicate the cause (diagnosis)
- Caregiver burden with the economic questionaries .
- Economics evaluation, Index 3

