9.4 EVALUATION AT 12 MONTHS OF DISCHARGE

Re-evaluate the following aspects by phone

- Mortality
- Functionality data (Barthel index, Lawton index , PASE Scale).
- Usual medication.
- Residency at the moment.
- Frailty with the FRAIL scale. Datos de fragilidad con la escala FRAIL.
- Data of quality of life with the scale EuroQolfive-dimensional (EQ-5D)
- Number of hospitalization and ER, indicate the cause (diagnosis)
- Burden of the caregiver with the economics questionnaires.
- Economics evaluation., Index 3

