9.5 END OF THE STUDY EVALUATION

- The study will finish at 12 months after patient's discharge with a lastphone call .
- We should make an effort to write all the data during the study, at follow up and the final evaluation..

A follow-up and investigator's tasks schedule was performed during the study. See table 2.

Table 2 Schedule of the investigation

Intervention phase	Eligibility&recruitment	Initial Visit	Discharge	3 month Follow-up	12 month Follow-up
Informed consent	X				
Eligibility CI and CE	X	X			
Medical history		X			
Usual treatment		X	X	X	X
Comprehensive Geriatric Assessment		X			
Cognitive and depression (MMSE,GDS,CAM)		X			
Comorbidities - Charlson I.		X			
Functional Status (Barthel I, Lawton I, PASE, SPBB)		X SPBB	X Barthel	X	X
Sociodemographic data		X			
Physical Exam		X			
Nutritional Status (MNA)		X			
Permanent residence		X	X	X	X
Mean hospital stay			X		
Death			X	X	X
Frailty (Fried)		X	X		
Frailty(FRAIL)		X	X	X	X
EuroQolfive-dimensional (EQ-5D)		X	X	X	X
Caregiver burden		X	X	X	X
Relocation to other hospital services			X		
Adverse events (iatrogenic, falls, geriatric syndromes, etc.)		X	X		
Economics evaluation			X	X	X
Checklist of complementary test during the hospitalization			X		
Consultation to other specialist during hospitalization			X		

Coordination of care in different levels of care		X		
Readmission			X	X
Visits to the emergency room			X	X
Nosocomial infections		X		

* In case of surgical patients, who after 3 weeks since the first visit have passed and surgery hasn't been performed, evaluate the possibility of re-assessing inclusion criteria.

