Complementing the main cost-effectiveness analysis, we will develop several parallel cost effectiveness analysis to the extent that effective change. The results that we will use are: hospitalization rate and readmission, lenght of hospitalization and in the Emergency department, episodes of delirium and nosocomial infection, post-surgical complications as a whole and by surgical procedure, number of inappropriate drugs, adherence to treatment, permanent institutionalization rate, survival rate, preventable side effects due to under / over / mismanagement on caregiver burden.

Cost-utility analysis:

Cost-utility analysis (ACU) is an evolution of cost-effectiveness analysis, in which the interference effects are measured in a unit that synthesizes the lifespan and quality of life. The best and better known measure is the quality of life-adjusted per quality (QALY QALY or in its Anglo-Saxon sense). The QALYs are calculated by weighting the survival time (years of age) with quality adjustment thereof, called utility, which represents the preference values in relation to different health states (reference). For the purpose, the EQ-5D-5L instrument will be used. The incremental cost-utility relation answers the following expression:

$$\text{ACU}_{\text{incremental}} = (C_a - C_b) / (\text{AVAC}(a) - \text{AVAC}(b))$$

Statistical analysis:

A descriptive analysis of the main resources used in health care, social services and informal care will be performed.

This includes basic statistics such as means, medians, standard deviations, skewness, kurtosis, ranges, bivariate analysis using different cost elements and individual characteristics (sex, age,...) and health outcomes.

Because different distributions are expected from major cost components, we hope to develop different multivariate estimation methods. As we expect a non-normal distribution of the estimated costs, an alternative analysis would be the use of GLM models grouped by clusters, where depending on the distribution of the estimated costs (distribution Gamma, Poisson or Gaussian), will be used the most suitable method of empirical analysis. Another alternative, if the necessary information is obtained, could be an analysis using multilevel models of 2 or 3 grade (Recital country and center). The costs

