Detach the next page along the lengthwise perforation, and then tear it in half along the horizontal perforation. Use the upper half of the page (blank) for the Comprehension, Writing, and Drawing items that follow. Use the lower half of the page as a stimulus form for the Reading ("CLOSE YOUR EYES") and Drawing (intersecting pentagons) items.

COMPREHENSION

Listen carefully because I am going to ask you to do something.

Take this paper in your right hand [pause], fold it in half [pause], and put it on the floor (or table).

TAKE IN RIGHT HAND _____ 0 1
FOLD IN HALF _____ 0 1
PUT ON FLOOR (or TABLE) _____ 0 1

READING

Please read this and do what it says. [Show examinee the words on the stimulus form.]

CLOSE YOUR EYES _____ 0 1

WRITING

Please write a sentence. [If examinee does not respond, say: Write about the weather.]

0 1

Place the blank piece of paper (unfolded) in front of the examinee and provide a pen or pencil. Score 1 point if the sentence is comprehensible and contains a subject and a verb. Ignore errors in grammar or spelling.

DRAWING

Please copy this design. [Display the intersecting pentagons on the stimulus form.]

0 1

[figure not shown]
Score 1 point if the drawing consists of two 5-sided figures that intersect to form a 4-sided figure.

Assessment of level of consciousness.

Total Score =
(Sum all item scores.) _____
(30 points max.)

Alert/ Responsive	Drowsy	Stuporous	Comatose/ Unresponsive

CLOSE YOUR EYES

ANEXO 3

Patient's information obtained from his/her clinical record

(Baseline)

1. **Patient's ID:** _____
2. (Register the generic names and total daily dose of drugs that the patient has taken during the last month)

		
		

3. 3. Hospitalization

What was the main cause of hospitalization?

	Diagnosis related Code Group (GRD)	GRD description	Mean stay (days)
			

Questionnaire for the subject(baseline)

1. **Identification number** _____

2. **Level of studies completed**

- Can read and write
- Primary
- Secondary
- University
- None

3. **Is the place where you live of your property?**

- Yes
- No

4. **Number of household members where the subject lives:** _____

people

5. **Carer**

a. **Do you need a carer to assist you with your daily activities?** (for basic hygiene, to help you to move, administration of drugs, performing treatments, etc. Monitoring and supervision tasks are also included)

- Yes
- No ⇒ Skip to question #6

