QUESTIONNAIRE FOR THE CARER (first contact-baseline)

The subject's principal informal carer (NOT CONTRACTED) fills in the questionnaire.

The principal informal carer is the person who is in charge of the patient whose autonomy has been limited for health reasons, and the person who spends more time with him/her or who has a greater responsibility to him/her compared with the other members of the patient's emotional environment.

1. Identification number: _____

2. Carer's date of birth (day/month/year): ____/____/19____

3. Sex:

Female

Male

4. Country: _____

5. Nationality: _____

6. Marital status:

Single Married or cohabiting Divorced Separated

Widow N/A

7. Level of studies completed:

Primary Secondary University None

8. What is your relationship with the subject? Are you his/her...

Sibling Grandchild Son/daughter Nephew/niece Friend

Neighbour Another (please specify) _____ N/A

9. Do you live with the care recipient?

Yes No

10. Since when have you cared for the subject?

 Less than 1 year	 between 4 and 6 years
 between 1 and 2 years	 More than 6 years
 between 2 and 4 years	 NA

HEALTH RELATED PROBLEMS**11. Have you had any health-related problem for caring the subject in the last 12 months?**

YES
 NO → skip to question #13

12. In case of YES, please specify if you suffer any or some of the following problems (multiple choice option):

I am depressed
 I am in treatment because of caregiving
 I am extremely tired
 I have back pain

WORK-RELATED PROBLEM**13. What is your MAIN working situation?**

I am employed
 I am unemployed

- Retired or pensioner ⇒ Skip to question #16
- Domestic tasks ⇒ Skip to question #17
- N/A ⇒ Skip to question #17

14. Have you had any work-related problem for caring the subject in the last 12 months?

- Yes
- No ⇒ Skip to question #16

15. In case of yes, please specify this

- I requested ____ days leave of absence
- I was working ____ hours less a day for ____ days
- I am working ____ hours less a day
- I do not work less hours a day but I have problems fulfilling my working hours
- I had to leave work because of illness the person I care
- Other problems: _____

16. Retirement (only to be answered in case the carer is retired or a pensioner)

a. Have you had to retire early to care for the subject?

- Yes
- No ⇒ Skip to question #17

b. In case of yes, please specify:

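### No economic assessment is scheduled at the initial visit although Annex 3 holds baseline subject and carer questionnaires, so baseline formal and informal care use may be missing or recorded too late to adjust costs

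*Combined protocol and SAP*

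**What the plan says.** **Schedule.** In Table 2 (section 9.5) the row "Economics evaluation" is blank under eligibility and under the initial visit, and marked at discharge, 3 months and 12 months. The visit text agrees: section 9.2 has "Economics evaluation Index 3", section 9.3 "Economics evaluation, Index 3" and section 9.4 "Economics evaluation., Index 3". Section 9.1, the baseline visit, has no such entry.

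**What 9.1 does collect.** Its demographic list includes the caregiver and "number of hospitalization in the last year, follow up by others specialist, level of education". It also records regular medication before admission, and assesses caregiver burden with the Modified Caregiver Strain Scale.

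**Forms.** Annex 3 (within section 11) contains a clinical-record form marked as baseline, a "Questionnaire for the subject(baseline" form and a "QUESTIONNAIRE FOR THE CARER (first contact-baseline" form. The subject form asks for weekly hours and payment of a professional carer, and for days of social services over the past month and past six months. The carer form asks for hours and minutes of unpaid care per day and per week. Further carer forms follow for weeks 12 and 52.

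**Analysis.** Section 10 builds total cost from direct health care, formal care and informal care. Its ICER definition measures benefits as change from baseline and says nothing comparable for costs. The descriptive paragraph mentions "bivariate analysis using different cost elements and individual characteristics (sex, age,...) and health outcomes". The models that follow (GLM, multilevel, log-normal or least squares, probit) come without a covariate list.

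**The concern.** The schedule and the annex disagree. The annex holds forms meant for baseline, and no visit before discharge is assigned to them. A site working from Table 2 and section 9.1 would have no instruction to use them at the first visit.

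Patients can enter with very different amounts of help already in place. Eligibility excludes nursing-home residents and a Barthel score below 40, but otherwise leaves room for anything from no help to regular paid or family care. Care received before randomisation may predict care received afterwards. If it is measured beforehand, it can absorb part of the patient-to-patient variation in formal and informal care costs. If it is not, a chance imbalance stays in the between-arm difference and the interval is wider than it need be. The societal perspective is a stated objective and counts both of these components. Pre-intervention values cannot be reliably reconstructed later.

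**Working it through.** The plan states no figure on this point, so there is nothing to reproduce. The check is a comparison of sections, followed by an illustration of size.

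**Step 1. Is the omission real?** Table 2 and the visit text can be compared independently.

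| Visit | Table 2 | Visit text |
|---|---|---|
| Initial visit | blank | not listed in 9.1 |
| Discharge | marked | listed in 9.2 |
| 3 months | marked | listed in 9.3 |
| 12 months | marked | listed in 9.4 |

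The two sources agree at every visit, so the blank is not a broken table cell.

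**Step 2. Which baseline quantities have no scheduled collection?**

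| Cost component (section 10) | Baseline information under 9.1 | Only in the Annex 3 baseline questionnaires |
|---|---|---|
| Direct health care | prior-year admissions, specialist follow-up, medication | little further |
| Formal care | none in quantity | professional-carer hours and payment, social-service days |
| Informal care | whether there is a caregiver; strain score | hours and minutes of care |

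The gap concerns two of three components.

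**Step 3. Does another Table 2 row close the gap?** Caregiver burden is marked at the initial visit, and 9.2 to 9.4 measure burden with the economic questionnaires, so that mark could be read as covering the carer form. For baseline, however, 9.1 names only the strain scale. Its 13 items record no care hours and no service days. On no reading does that row cover the subject's social services.

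**Step 4. Do the form headings secure the timing?** Not fully. The week-12 and week-52 carer forms tell a new or first-contact carer to fill in the baseline form at that point, so it may first be completed months after randomisation. If the baseline forms are instead used at discharge, the one-month window for social services can overlap the index stay, and the intervention has already begun.

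**Step 5. What would adjustment gain?** For linear adjustment of a continuous outcome on one baseline covariate with correlation r to the outcome:

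- share of variance removed = r²
- standard-error ratio = √(1 − r²)

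The documents give no r. Over an assumed range:

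| r | Variance removed | SE ratio |
|---|---|---|
| 0.1 | 1% | 0.995 |
| 0.3 | 9% | 0.954 |
| 0.5 | 25% | 0.866 |
| 0.7 | 49% | 0.714 |

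These figures apply to the difference in one care component. For total cost, suppose that component contributes a share s of the total variance, is uncorrelated with the rest, and its baseline value predicts nothing else. The share removed is then s·r², which is below r² whenever s is below 1. The documents do not give s.

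**The case against.** The strongest reply is that the forms and the schedule may fit together after all. Annex 3 has no separate discharge form, yet 9.2 calls for the economic assessment at discharge. The baseline set may be intended for then. The record form supports this: it asks for the diagnosis group and the stay, which are known only at the end of admission. The subject form looks back over one, six and twelve months, so prior use could be captured by recall. This is a possible reading, but the documents do not state it. It would place a form called baseline after the start of the intervention, and the carer form asks about a normal day or week with no look-back period. What stands is that loss is a risk rather than a certainty, and that the record form's stay and diagnosis-group items cannot move to the first visit.

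A reader might infer three stronger things that the documents do not support:

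- **That baseline resource use is lost altogether.** Section 9.1 keeps prior admissions, specialist follow-up, medication and presence of a caregiver.
- **That section 10 rules out prior use as a covariate.** The phrase "bivariate analysis using different cost elements and individual characteristics (sex, age,...) and health outcomes" is an open-ended item in a descriptive paragraph, not a model specification. The models list no covariates, and country and centre already appear as possible multilevel terms.
- **That the cost comparison is biased without adjustment.** Allocation is randomised 1:1. Chance imbalance is ordinary sampling error and the interval already reflects it.

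The objection on size also stands in part. The r² formula is for linear models, whereas section 10 foresees probit models for formal and informal care costs and gamma or Poisson GLMs for costs. The health-system perspective counts direct health costs only, so formal and informal care are not components there.

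**Conclusion.** The point holds as a gap between schedule and forms, with a consequence for precision. Table 2 and section 9.1 schedule no economic assessment at the initial visit, while Annex 3 supplies baseline subject and carer questionnaires. As scheduled, baseline formal and informal care use may be missing or first recorded at discharge or later, and section 10 does not say that it would be used.

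The size is uncertain. It rests on an assumed correlation of 0.1 to 0.7 and on linear adjustment, which give a variance reduction of 1% to 49% for the difference in one care component. At the top of that range one could be tempted to say that adjustment nearly doubles the effective sample size, since 1/(1 − 0.49) = 1.96. That cannot be carried over to total cost, which includes inpatient care, or to the ICER, which also carries the uncertainty of its denominator. There the gain is smaller or unknown.

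This is a worthwhile, inexpensive improvement to a secondary economic analysis. It is not an error that invalidates it.

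**What to change.** 1. In Table 2, mark the economic evaluation at the initial visit.
2. In section 9.1, list the Annex 3 baseline subject and carer questionnaires, to be completed before the intervention starts and, where possible, before the arm is known. Leave the record form's hospital-stay and diagnosis-group items at discharge.
3. In section 10, state that the between-arm comparisons of formal, informal and societal costs are adjusted for baseline formal and informal care use, with centre and clinical setting.

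The cost is one table entry and a few sentences, because the questionnaires already exist. The downside is extra questionnaire time for patient and carer at the first visit.

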10 ECONOMIC EVALUATION

An economical evaluation of the program will be conducted to detect and handle the frail elderly in different health areas. We will conduct a comparative analysis in terms of costs and benefits of a geriatrician's intervention compared with usual care.

Information on both patients and caregivers about health resources and social services use and time spent by the caregiver will be collected. The next step is to translate this resource consumption in monetary terms. The costs will be reported in euros and in places where it is not used this coin the current exchange will take place.

The total cost is the sum of three different types of costs: directly deriveate from care; formal care costs (professional) and informal care costs (family and friends)

Direct health care costs:

These costs are related to inpatient treatment, outpatient treatment, medicines, etc. These are estimated from the use of health services by assigning a monetary value for each resource used.

Health resources will be identified and measured through questionnaires. Each center will give us the price or the monetary value of each resource. If some of this information is not available, it will be obtained from a systematic review of studies of cost of illness for each country.

Formal care costs (Social Services):

Formal care includes those generated by social services which can be public or privately funded institutions such as day care centers, remote assistance, scheduled home care, etc. These costs will be identified, measured and evaluated through questionnaires. Ideally, members of each research team from each center must provide to the economic team price and monetary values (unit costs) of resources for social services.

If data about unit cost of social services are not available, a review of the literature will be performed to obtain the data by country.

Social costs (informal care)

Informal care includes different types of unpaid support which serve to compensate for the inability of subjects, usually provided by relatives or friends. This information is obtained from questionnaires applied directly to caregivers in which time spent on helping the elderly in basic Activities of Daily Living and Instrumental Activities will be specified. The time spent on these activities will be evaluated in monetary terms using 'proxy goodmethod "or" replacement method "which assesses the time spent on informal care adjusted to market prices of a professional who has to do this work (social service Careful formal).

The economic evaluation will be developed to take into account several aspects: financing health care (including only direct health costs), finance formal care (including the direct costs of health and social services) and social perspective (including all relevant costs: direct medical care + formal care (social services) and informal care.

Outcome measures:

Cost-effectiveness analysis

The cost-effectiveness analysis (CEA) is the most common test used in health economics to decide between different treatments for the same condition. In a CEA, the costs are measured in monetary units, while the benefits are measured as outcomes or in natural units. "Incremental cost-effectiveness ratio" (ICER) is estimated to show a difference in health outcomes per unit cost, after a follow-up period between intervention and usual care. The incremental cost-effectiveness is expressed by the following relation:

$$ICER = \frac{C_a - C_b}{B_a - B_b}$$

Where Ca is the cost of the intervention group and Cb is the cost of the usual care group. Ba will be health benefits in the intervention group and Bb health benefits in the usual care group, both measured in terms of change of the clinical results of the baseline.

In this study the primary outcomes will be the difference in functional status after the intervention compared with usual care group. This study will assess the cost-effectiveness of the intervention of a geriatrician compared with usual care from the perspective of society and the health care system.

Complementing the main cost-effectiveness analysis, we will develop several parallel cost effectiveness analysis to the extent that effective change. The results that we will use are: hospitalization rate and readmission, lenght of hospitalization and in the Emergency department, episodes of delirium and nosocomial infection, post-surgical complications as a whole and by surgical procedure, number of inappropriate drugs, adherence to treatment, permanent institutionalization rate, survival rate, preventable side effects due to under / over / mismanagement on caregiver burden.

Cost-utility analysis:

Cost-utility analysis (ACU) is an evolution of cost-effectiveness analysis, in which the interference effects are measured in a unit that synthesizes the lifespan and quality of life. The best and better known measure is the quality of life-adjusted per quality (QALY QALY or in its Anglo-Saxon sense). The QALYs are calculated by weighting the survival time (years of age) with quality adjustment thereof, called utility, which represents the preference values in relation to different health states (reference). For the purpose, the EQ-5D-5L instrument will be used. The incremental cost-utility relation answers the following expression:

$$\text{ACU}_{\text{incremental}} = (C_a - C_b) / (\text{AVAC}(a) - \text{AVAC}(b))$$

Statistical analysis:

A descriptive analysis of the main resources used in health care, social services and informal care will be performed.

This includes basic statistics such as means, medians, standard deviations, skewness, kurtosis, ranges, bivariate analysis using different cost elements and individual characteristics (sex, age,...) and health outcomes.

Because different distributions are expected from major cost components, we hope to develop different multivariate estimation methods. As we expect a non-normal distribution of the estimated costs, an alternative analysis would be the use of GLM models grouped by clusters, where depending on the distribution of the estimated costs (distribution Gamma, Poisson or Gaussian), will be used the most suitable method of empirical analysis. Another alternative, if the necessary information is obtained, could be an analysis using multilevel models of 2 or 3 grade (Recital country and center). The costs

of health care could also be analyzed by a normal multivariate model (clustering) or log-normal and the ordinary least square regression will be used to estimate the determinants of health care costs. In contrast, for the analysis of formal and informal care costs, we expect to use simple probit or ordered probit models, whether formal and informal care for a large number of people in the study is provided.

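### No baseline-utility adjustment is specified for the QALY difference, the ICER effect is a raw change score, and neither economic ratio has a planned measure of uncertainty

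*Combined protocol and SAP*

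**What the plan says.** All references are to the combined protocol and SAP.

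- **QALY and cost-utility ratio (section 10).** "The QALYs are calculated by weighting the survival time (years of age) with quality adjustment thereof, called utility". On the instrument: "For the purpose, the EQ-5D-5L instrument will be used". The ratio is introduced by "The incremental cost-utility relation answers the following expression", followed by the cost difference divided by the QALY difference. No covariate is named.
- **Cost-effectiveness ratio (section 10).** The ICER "is estimated to show a difference in health outcomes per unit cost, after a follow-up period between intervention and usual care". The benefits in its denominator are "both measured in terms of change of the clinical results of the baseline".
- **Models (section 10, statistical analysis).** "Because different distributions are expected from major cost components, we hope to develop different multivariate estimation methods". The GLM, multilevel, log-normal, least-squares and probit models that follow are all for cost components. Health outcomes appear only in a list of descriptive and bivariate summaries.
- **Baseline data.** Section 9.1 schedules "The evaluation for the quality of life using the EuroQol five-dimensional (EQ-5D), Index 2". Table 2 repeats EQ-5D at discharge, 3 months and 12 months. Barthel, Lawton and PASE are listed at baseline and at both telephone follow-ups (sections 9.1, 9.3, 9.4).
- **Main analysis.** Section 7.4 plans a Mann-Whitney test between arms and expects any difference to come from the intervention. Section 7.2 gives 1:1 allocation and mentions no stratification.
- **Uncertainty.** No interval, bootstrap, cost-effectiveness plane, acceptability curve or net-benefit analysis is described for either ratio.

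**The concern.** There are two separate gaps.

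The first is how baseline values are used. Utility at admission is likely to predict later utility, so a chance difference between arms at baseline will partly reappear in the QALY difference. The covariate that would remove it is already collected, but no analysis uses it. For the functional effect the plan does use baseline, by subtracting it. That fixes the slope of follow-up on baseline at 1. If the true slope is lower, the change score takes off too much and favours the arm that started worse.

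The second is that both ratios are given only as formulas. A ratio whose denominator may be close to zero cannot support a conclusion on cost-effectiveness without a statement of its uncertainty.

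Cost-effectiveness and cost-utility are stated objectives (section 3.2) and secondary outcomes (section 4.2). EQ-5D quality of life is also listed as a primary outcome (section 4.1).

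**Working it through.** **Numbers per arm.** The plan gives no figure for QALYs or for either ratio, so its sample size serves only to supply n. Section 7.3 asks for at least 40 events at incidence 0.40: n = 128 gives 128 × 0.40 − 1.96 × √(128 × 0.40 × 0.60) = 40.3, and n = 127 gives 39.98. Adding 20% gives 128 × 1.2 = 154, close to the stated 155 per arm. The total of 1860 equals 310 × 6. The section names five settings; Table 1 lists elective and emergency surgery separately, which would make six. I use the stated total:

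- pooled: 1860 / 2 = 930 per arm, and 930 × 0.8 = 744 after 20% drop-out;
- one setting: 155 per arm, and 155 × 0.8 = 124 after drop-out.

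**Assumptions, none of them in the documents.** Utility SD 0.20 to 0.30; slope b of QALY on baseline utility 0.3 to 0.7; correlation r 0.3 to 0.7.

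**Shift in the QALY difference.** The 95% limit of a chance baseline difference is 1.96 × SD × √(2/n). The shift is b times that.

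| n per arm | SD | 95% limit | shift, b = 0.3 | b = 0.5 | b = 0.7 |
|---|---|---|---|---|---|
| 930 | 0.20 | 0.018 | 0.005 | 0.009 | 0.013 |
| 744 | 0.25 | 0.025 | 0.008 | 0.013 | 0.018 |
| 744 | 0.30 | 0.030 | 0.009 | 0.015 | 0.021 |
| 155 | 0.20 | 0.045 | 0.013 | 0.022 | 0.031 |
| 124 | 0.30 | 0.075 | 0.022 | 0.037 | 0.052 |

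The pooled range is therefore 0.005 to 0.021, and the range within one setting 0.013 to 0.052. These are limits. The mean absolute imbalance is about 0.80/1.96 = 41% of the limit; at SD 0.25, b = 0.5 and 744 per arm that is 0.41 × 0.0127 = 0.005 QALY.

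**On average and conditionally.** In 20,000 simulated trials with no true effect (124 per arm, SD 0.25, slope 0.5), the mean unadjusted difference was about 0 overall. It was +0.038 in the trials whose baseline difference exceeded the upper 95% limit.

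**Precision.** Adjustment multiplies the variance by 1 − r², a cut of 9%, 25% or 49% at r = 0.3, 0.5 or 0.7. The SE ratios are 0.95, 0.87 and 0.71. With a QALY SD of 0.25 and 744 per arm, the 95% half-width falls from 0.025 to 0.024, 0.022 or 0.018.

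**Route of the carry-over.** Follow-up is timed from discharge. Under a trapezoidal area through baseline, discharge, 3 and 12 months, baseline utility is weighted by half the stay. Length of stay is not given. For assumed stays of 10 and 30 days the weights are 5/365 and 15/365 of a year, so an imbalance of 0.030 contributes directly 0.0004 and 0.0012 QALY. The rest of the shift must come from correlation between admission utility and later utility.

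**Change score.** With slope β = r × SD(follow-up)/SD(baseline), the large-sample variance of a change score is proportional to SD(follow-up)² × (1 − r²) + SD(baseline)² × (β − 1)². The first term is the variance after baseline adjustment, so the change score is never more precise. With equal SDs the comparison is 2(1 − r) against 1 − r²: 1.40 against 0.91 at r = 0.3, 1.00 against 0.75 at 0.5, and 0.60 against 0.51 at 0.7. The change score carries (β − 1) times the baseline difference, which is −0.5 times it at β = 0.5.

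**Missing interval, as an illustration only.** Assume a true difference of 0.03 QALY and 600 euro, a ratio of 20,000 euro per QALY. The pooled half-width of 0.0254, with cost held fixed, spans 600/0.0554 = about 10,800 to 600/0.0046 = about 130,000. An imbalance shift of ±0.0127 alone moves the ratio to about 14,100 or 34,700.

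**The case against.** The strongest reply is that the quoted sentence only defines a QALY and the displayed ratio is the standard definition of an incremental ratio. Neither says how the QALY difference will be estimated. That stands. A reader might infer that the plan chooses an unadjusted comparison; the documents are silent on adjustment and do not reject it. The silence still matters, because the choice stays open until the data have been seen.

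Second, randomisation keeps the unadjusted difference unbiased on average, and a valid interval would already cover chance imbalance. This also stands: adjustment is a gain in efficiency and in protection against imbalance, not the repair of an invalid estimator. But no such interval is planned.

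Third, a reader might infer that imbalance enters because the QALY total contains baseline utility. The stay-length calculation shows that this direct part is very small, so the size rests on an undocumented correlation.

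Fourth, it is tempting to say that change scores over-correct whenever the correlation is below 1. The condition is a slope below 1. Section 6.2 excludes Barthel below 40 at entry while follow-up Barthel is unrestricted, so the SD ratio may exceed 1 and over-correction is plausible but not certain.

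Finally, the per-setting figures apply only if the economic analysis is run by setting. Section 7.4 plans effects by setting, but section 10 does not explicitly plan a cost-utility ratio by setting.

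**Conclusion.** The point holds as a worthwhile improvement rather than a flaw in validity. No baseline adjustment is specified for QALYs, the functional effect uses a change score that baseline adjustment equals or beats in large samples, and no uncertainty is planned for either ratio. The last is a separate gap: a missing interval hides uncertainty but does not itself let baseline imbalance into the estimate.

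Under the assumed SDs and slopes, an imbalance at the 95% limit moves the pooled QALY difference by about 0.005 to 0.021, and a typical imbalance by much less. The variance reduction runs from 9% to 49%, depending wholly on a correlation the documents do not give; at the low end the gain is modest. The documents do not support a claim that the planned QALY comparison is biased.

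**What to change.** Amend section 10 as follows.

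1. Estimate the QALY difference by regressing the area under the EQ-5D utility curve (all scheduled assessments, utility 0 from death) on arm, baseline utility, setting and centre.
2. Replace the change score for functional effect with the follow-up score adjusted for its baseline, using scales scheduled at follow-up (Barthel, Lawton, PASE). Sections 9.2 to 9.4 do not list SPPB after baseline. State how deaths and incomplete series are handled, given the 20% drop-out assumed in section 7.3.
3. Report 95% bootstrap intervals for the cost and effect differences, resampling each patient's cost and effect together within centre, and add an acceptability curve.
4. Reconcile the last follow-up. Section 7.2 gives the sixth month; sections 9.4 and 9.5 and Table 2 give 12 months. The QALY horizon depends on it.

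Items 1 to 3 change analysis wording only and need no new data. Item 4 is a consistency correction.
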